5.3 Concomitant Medications/Treatments

Systemic corticosteroids greater than the equivalent of 10 mg of prednisone or equivalent alternative steroid (except physiologic dose for adrenal replacement therapy) or other immunosuppressive agents (such as cyclosporine or methotrexate) and any other medications that could potentially impact the efficacy or safety of the study as judged by the treating investigator are NOT permitted from time of registration to subjects completing protocol therapy unless clinically indicated to manage adverse events or life threatening or serious conditions as determined by the treating investigator.

Subjects are prohibited from receiving the following therapies during the Screening and Treatment Phase of this trial:

- Immunotherapy not specified in this protocol
- Chemotherapy not specified in this protocol
- Investigational agents other than ESK981 or checkpoint inhibitor immunotherapy
- Neulasta®
- Live vaccines within 30 days prior to the initial study treatment administration through the last dose of study treatment. Examples of live vaccines include, but are not limited to, the following: measles, mumps, rubella, varicella/zoster, yellow fever, intranasal influenza, rabies, BCG (tuberculosis vaccine), and typhoid vaccine.
 - If precluded by local regulations, live vaccines should not be given for 120 days after the last dose of checkpoint inhibitor immunotherapy is administered.
- Systemic glucocorticoids or other immunosuppressive drugs for any purpose other than to modulate symptoms from a drug-related AE of immunologic etiology (refer to Section 5.2 – Dose Modification). The use of physiologic doses of corticosteroids may be approved after consultation with the Study PI.
 - Use of prophylactic corticosteroids to avoid allergic and other adverse reactions (e.g., to IV contrast dye or transfusions) is permitted.
 - Use of intermittent inhaled steroids or local injection of corticosteroids is permitted upon consultation with the Principal Investigator.
 - Physiologic doses of prednisone ≤10 mg (or equivalent) per day.

5.4 Other Modalities or Procedures

No other modalities or procedures will be used in this protocol.

5.5 Duration of Therapy

In the absence of treatment delays due to adverse events, treatment may continue until one of the criteria listed in Section 5.6 apply. Patients will be followed for up to 24 months after removal from treatment or until death, whichever occurs first. Patients removed from treatment for unacceptable adverse events will be followed by phone call or clinic visit until resolution or stabilization of the adverse events.

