8.6	Serious Adverse Event Reporting Guidelines	40
8.7	Routine Reporting	41
8.8	Reporting of Unanticipated Problems	41
8.9	Early Stopping Rules.....	41
9.0	DRUG INFORMATION	41
9.1	ESK981	41
9.2	Nivolumab.....	48
10.0	SPECIAL STUDIES.....	49
10.1	Sample Collection Guidelines	49
10.2	Specimen Banking	49
11.0	STATISTICAL CONSIDERATIONS	49
11.1	Study Design/Study Endpoints.....	50
11.2	Sample Size and Accrual.....	50
11.3	Early Stopping Due to Toxicity.....	50
11.4	Data Analyses Plans	50
12.0	DATA MANAGEMENT	51
13.0	DATA AND SAFETY MONITORING.....	51
14.0	QUALITY ASSURANCE AND AUDITS	52
15.0	CLINICAL MONITORING PROCEDURES	52
16.0	REFERENCES.....	54
APPENDICES.....		56
APPENDIX 1	Karnofsky Performance Scale.....	56
APPENDIX 2	Medications with the Potential for Drug-Drug Interactions	57
APPENDIX 3	Study Management During COVID-19	59

ABBREVIATIONS

AE	Adverse Event
ALT	Alanine Aminotransferase
ALC	Absolute Lymphocyte Count
AST	Aspartate Aminotransferase
BUN	Blood Urea Nitrogen
CBC	Complete Blood Count
CMP	Comprehensive Metabolic Panel
CR	Complete Response
CT	Computed Tomography
CTCAE	Common Terminology Criteria for Adverse Events
CTSU	Clinical Trials Support Unit
DLT	Dose Limiting Toxicity
DSMC	Data and Safety Monitoring Committee
ESK981	Study Drug
H&P	History & Physical Exam
HRPP	Human Research Protections Program
IND	Investigational New Drug
IRB	Institutional Review Board
IV (or iv)	Intravenously
MTD	Maximum Tolerated Dose
NCI	National Cancer Institute
ORR	Overall Response Rate
OS	Overall Survival
PBMCs	Peripheral Blood Mononuclear Cells
PD	Progressive Disease
PFS	Progression Free Survival
PI	Principal Investigator
p.o.	per os/by mouth/orally
PR	Partial Response
PRC	Protocol Review Committee
RCC	Renal Cell Carcinoma
SAE	Serious Adverse Event
SD	Stable Disease
SGOT	Serum Glutamic Oxaloacetic Transaminase
SPGT	Serum Glutamic Pyruvic Transaminase
UaP	Unanticipated Problem
WBC	White Blood Cells

STUDY SCHEMA

STUDY SYNOPSIS

Title	ERICa: Phase 2 Multi-Center Trial Of ESK981 and Nivolumab In Patients With Metastatic Renal Cell Carcinoma
Phase	II
Methodology	Single arm; two cohorts
Study Duration	54-60 months (24-30 months for accrual, estimated 6 months for treatment, and 24 months of follow-up)
Study Center(s)	Multi-Center: 2 sites total including lead site: University of Michigan

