	
 • History of gastrointestinal perforation or fistula in the past 6 months, or while previously on antiangiogenic therapy, unless underlying risk has been resolved (e.g. through surgical resection or repair). • The patient has known hypersensitivity to gelatin or lactose monohydrate. • The patient has received any investigational drug within 28 days prior to registration or 5 half-lives of the investigational drug, whichever is shorter. • History of bleeding disorders (e.g. pulmonary hemorrhage, significant hemoptysis, menometrorrhagia not responding to hormonal treatment) ≤ 6 weeks before Cycle 1 Day1. • The patient is on a chronic daily medication known to be a severe or moderate inhibitor or inducer by Micromedex of CYP1A2, CYP2C8, or CYP3A4 at registration. • Systemic corticosteroids greater than the equivalent of 10 mg of prednisone or equivalent alternative steroid (except physiologic dose for adrenal replacement therapy) or other immunosuppressive agents (such as cyclosporine or methotrexate) and any other medications that could potentially impact the efficacy or safety of the study as judged by the treating investigator are NOT permitted from time of registration to subjects completing protocol therapy unless clinically indicated to manage adverse events or life threatening or serious conditions as determined by the treating investigator. • Have any condition that, in the opinion of the investigator, would compromise the ability of the subject to meet or perform study requirements.
Study Product(s), Dose, Route, Regimen	
Cohort A (n = 11) – ESK981 given PO 160 mg 5 consecutive days followed by a 2-day off drug in each week, repeated weekly in 28 day cycles
 
Cohort B (n = 36): ESK981 given PO 160 mg 5 consecutive days followed by a 2-day off drug in each week, repeated weekly in 28 day cycles in combination with nivolumab 480 mg IV on D1 every 28 day cycles as safety lead-in. If no safety signals are identified, we will accrue 19 additional subjects for a total of 36 subjects in the combination cohort B.

Duration of Administration	Until disease progression or intolerable toxicity or subject withdraws consent
Reference Therapy	None for Cohort A; Nivolumab alone (historical) for Cohort B

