While Ang2 may have a role in many tumor types, it may be particularly important in the tumorigenesis of renal cell carcinoma as demonstrated by the significantly higher levels of Ang2 in RCC as compared to other tumor types [27] (Figure 2).

[figure not shown]

Figure 2: RT-PCR analysis of multiple tumor types shows that Ang2, VEGF, Ang1, VEGFR2, and CD31 are highly expressed in patients with ccRCC *versus* other tumor types (bladder, lymphoma, lung, laryngeal, ovarian, prostate, gastric, breast, colorectal, and pancreatic tumors). Ang2 and VEGF are also highly expressed in ccRCC *versus* normal kidney tissue. Data are expressed as means \pm SD. * $P < 0.05$, ** $P < 0.01$, *** $P < 0.001$. [27]

Given the extensive pre-clinical data suggesting the deleterious effect of Ang-2 on tumor growth and angiogenesis, Ang2 inhibitors have been evaluated for the treatment of patients with metastatic renal cell carcinoma. In a phase II study by Atkins et al [28], trebananib (an Ang1/2 inhibitor) was combined with sunitinib for the treatment of treatment naïve metastatic renal cell carcinoma. This combination led to impressive response rates of 58-63%, notably higher than front line response rates with sunitinib or pazopanib of 25-31% [29] (Figure 3).

[figure not shown]
[figure not shown]

Figure 3: Maximum change from baseline in the sum of longest diameters (SLD) of target lesions at the time of the primary analysis for patients who received (A) trebananib 10 mg/kg once per week in cohort A or (B) trebananib 15 mg/kg once per week in Cohort B

Median overall survival was also improved as compared to

historical controls treated with sunitinib or pazopanib with a median overall survival of 36 months (as compared to historical controls of 28-29 months [29]). Unfortunately, the combination of these drugs was associated with increased toxicity as compared to sunitinib alone and the combination has not been further evaluated in metastatic renal cell carcinoma.

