6.0 SCHEDULE OF ASSESSMENTS

6.1 Time and Events Table

1 cycle (C) = 28 days (D).

Trial Period	Screening (-28 to -1 days)	C1D1	C2D1	C3D1	C4D1	Additional Cycles...	EOT ⁷	Follow-Up ⁸
							30 days from last dose (+/- 7 business days)	Every 12 weeks (+/-14 business days) for up to 24 months/death
Informed Consent	X							
Tumor tissue specimen (15 FFPE slides required; blocks preferred) identified	X							
Blood for banking		X						
History, PE, Concomitant Meds, Vital Signs ¹	X	X	X	X	X	X	X	
PT/INR, aPTT	X							
Karnofsky Performance Status	X	X	X	X	X	X	X	
Pregnancy Test for WOCBP ²	X							
Toxicity (include DLT) Evaluations ¹²	X	X	X	X	X	X	X	
CBC with differential, platelets ³	X	X ¹³	X ¹³	X	X	X	X	
COMP ⁴	X	X	X	X	X	X	X	
TSH	X	Every 12 weeks from Cycle 1 Day 1 ⁵						
QoL (EQ-5D-5L)		X	X	X		X ¹⁴		X
Pill Diary collection/handing out		X	X	X	X	X		
Tumor response assessment ⁶ (CT chest, CT or MRI abdomen/pelvis; CT or MRI brain if clinically indicated)	X			X		X ⁶		X
Treatment								
ESK98 ^{9, 10} (Cohort A and B)		X	X	X	X	X		
Nivolumab ¹¹ (Cohort B only)		X	X	X	X	X		
Survival Status								X

1. Vital signs will include weight, temperature, pulse, respirations, blood pressure; height will be obtained at screening only.
2. WOCBP: Women of child bearing potential; either urine or serum pregnancy test.
3. CBC with diff includes total WBC, hemoglobin, hematocrit and differential of the WBC including absolute counts. Other checks are at discretion of treating investigator.

4. COMP or Comprehensive metabolic profile includes sodium, potassium, chloride, bicarbonate, BUN, creatinine, AST, ALT, alkaline phosphatase, total bilirubin.
5. TSH: Every 12 weeks from Cycle 1 Day 1 (i.e. Cycle 4 Day 1; Cycle 7 Day 1, etc.).
6. Window of +/- 7 business days. Imaging will be with or without intravenous contrast, before or on associated visit. CT or MRI brain with (preferred) or without IV contrast if suspected or known brain metastases. Frequency of tumor assessments will be q2 cycles (i.e. q 8 weeks) for first 4 assessments beyond baseline and then q 3 cycles (i.e. 12 weeks) subsequently until withdrawal of consent/death/2 years from C1 D1 whichever is later. If CR/PD, should be confirmed with repeat imaging after an interval of at least 4 weeks. In follow-up, if subjects are on alternative therapies, no mandated imaging but data from routine imaging will be captured at least every 12 weeks if available (+/- 7 business days).

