11.4 Data Analyses Plans

The primary analysis of efficacy will report the number of patients with an objective response and the associated proportion with the corresponding 95% exact binomial confidence interval separately in each cohort. In Cohort B, if stage 2 is initiated then the efficacy analysis methods will be adjusted for the interim check as described by Koyama and Chen [36].

Toxicity will be described by grade, attribution, and body system using counts and proportions. Toxicity will be described separately for each cohort.

Overall survival, progression free survival, duration of therapy, and duration of response will be displayed using a Kaplan-Meier figure and the associated median (if reached), one-year and two-year estimates with 95% confidence intervals using Greenwood's formula will be reported if there is censoring. If there is no censoring in the endpoint, then the standard mean (or median) and 95% confidence interval (or 5th and 95th percentiles) will be reported. Each endpoint will be reported separately by cohort.

Health-related quality of life assessment changes from baseline using EuroQoL-5D will be described using descriptive statistics.

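### Survival follow-up ends 24 months after each patient stops treatment, so overall-survival censoring depends on time on treatment and the Kaplan-Meier curve after month 24 is thinned and probably reads high

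*Combined protocol and SAP*

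**What the plan says.** Section 5.5 sets the limit: "Patients will be followed for up to 24 months after removal from treatment or until death, whichever occurs first". In 6.1 the Follow-Up column, which carries the Survival Status row, reads "Every 12 weeks (+/-14 business days) for up to 24 months/death". Time on treatment is open-ended; the synopsis gives its duration as "Until disease progression or intolerable toxicity or subject withdraws consent".

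OS is a secondary endpoint (2.5.3). Section 11.4 states that "Overall survival, progression free survival, duration of therapy, and duration of response will be displayed using a Kaplan-Meier figure", and reports "the associated median (if reached), one-year and two-year estimates with 95% confidence intervals". Section 7.1.6 defines progression-free survival from the start of treatment. No section defines OS or says when a living patient is censored, and none follows survivors to a common date. The synopsis gives the study duration as "54-60 months (24-30 months for accrual, estimated 6 months for treatment, and 24 months of follow-up").

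**The concern.** Kaplan-Meier estimation assumes that patients who leave the risk set have the same prognosis as those who remain. Here the leaving date is set by when treatment stopped. A living patient who stops at month 2 leaves at month 26; one who stops at month 14 stays until month 38. Patients who stop early mostly do so because of progression or toxicity, and they are the first to go. The later curve then rests increasingly on long-treated patients, with fewer at risk.

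What is at stake is the right-hand part of the OS curve and, if the median falls there, the median itself. The rule serves tolerably if the combination only matches its historical reference and worsens as the combination improves on it. Early enrollees are also dropped while the study is still open.

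**Working it through.** **The plan's own figure.** Study duration = accrual + treatment + follow-up: 24 + 6 + 24 = 54 and 30 + 6 + 24 = 60 months. This reproduces the stated 54–60 months. By the same sum, a patient enrolled at month 0 and treated for 6 months leaves survival follow-up at month 30, with 24–30 months of the study still to run. The plan states no expected OS median and no OS event count, so there is no OS figure to reproduce.

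**Where the cap acts.** Let T be survival time and D time on treatment. Censoring is at C = D + 24, so nobody is censored by the cap before month 24, and the one- and two-year estimates are the same under either rule. After month 24,

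expected number at risk at t = n × P(T > t) × P(D > t − 24 given T > t).

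**Hand check, D and T independent.** Assume n = 36 (Cohort B, 11.1), exponential OS, and exponential D with a median of 6 months.
- True median 25, t = 25: survivors 36 × 0.5 = 18; at risk 18 × 0.5^(1/6) = 16.0. About 2 of 18 are lost.
- True median 29, t = 30: survivors 36 × 0.5^(30/29) = 17.6; at risk 17.6 × 0.5^(6/6) = 8.8. Half are lost.

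**Simulation with dependence.** Assumptions that the documents do not give: exponential distributions as above, Gaussian-copula correlation 0.3–0.7 between D and T, entry uniform over months 8–30, and closure at month 60. Month 8 lies within the 11/2 = 5.5 to 11/1 = 11 months that Cohort A's 11 patients need at the stated 1–2 per month. The current rule was run as C = min(D + 24, closure) and, where shown, as C = D + 24 with no closure date. The comparator follows every patient to closure.

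- *True median 25 months* (the nivolumab figure in 1.3). The large-sample Kaplan-Meier median is about 25. It is reached in about 91–93% of trials, against about 100% with common closure. At month 36 there are 3.4–4.9 patients at risk against 9.6.
- *True median 29 months.* The cap alone censors 12–14 of 36 patients alive. At month 30 about 10.5–13 are at risk against 17.6. The curve reads 44–46% at month 36 (true 42%) and 40–43% at month 42 (true 37%). The large-sample median is 29.4–30.1. The median is reached in about 76–82% of trials (80–88% with no closure date) against 97%.
- *True median 36 months.* The median is reached in about 43–55% of trials (46–68% with no closure date) against 86–87%. Its large-sample value is about 39 months at correlation 0.3, about 42 at 0.5, and not reached at 0.7.
- *Zero correlation.* There is no bias. Only the loss of patients at risk remains, as in the hand check.

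**Sensitivity.** A second simulation used entry over months 8–27, closure at month 57, mean or median treatment time of 6 months, and correlation 0 or 0.5. The median was reached in 87–93% against 99% of trials (true median 25), 64–78% against 93–95% (true median 30), and 38–60% against 80–84% (true median 36). Deaths observed rose by about 3–4 of 36 under common closure.

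**The case against.** A reader might infer that the cap removes patients exactly where the median OS is expected. The documents do not support that, because they state no expected OS median. The synopsis names nivolumab alone as Cohort B's historical reference, and its figure in 1.3 is 25 months, where the median is hardly touched. The longer figures in 1.1, "a median overall survival of 36 months (as compared to historical controls of 28-29 months", belong to other regimens in untreated disease and are not benchmarks for this trial. This objection stands, and it limits the point to the case where the combination improves on its reference.

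Other objections stand in part:
- The correlation has no source in the documents. Its direction follows from the reasons for which treatment stops; its size is assumed.
- The synopsis's 6 months is an estimate, not a stated median or distribution.
- At a true median of 29 months the bias at month 36 is 2–4 percentage points, against a sampling standard deviation of about 8 points with 36 patients (√(0.42 × 0.58/36) = 0.08).
- Part of the simulated loss comes from a closure date that 5.5 does not impose. The figures without it are smaller, but the shortfall remains.
- OS is secondary and descriptive, with no test attached, and 11.4 already allows for a median that is not reached.

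One objection fails. Footnote 6 of 6.1 continues imaging to the latest of withdrawal, death or two years from first dose, which might seem to keep survivors under observation. It governs scans, and it lifts mandated imaging for patients on other therapies. It does not extend survival status.

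**Conclusion.** The point holds as a low-cost improvement to a secondary endpoint. The rule ties OS censoring to time on treatment, thins the risk set after month 24 and, if time on treatment and survival are positively correlated, biases the curve upward there. At a true median near 25 months the effect on the median is minor. From about 29–30 months upward it is material: the median is missed in roughly one trial in five at 29 months and in about half at 36 months, under the stated assumptions. A reader might go further and conclude that the trial's efficacy conclusion is at risk. It is not: the response-rate decision and the one- and two-year OS estimates do not depend on this rule.

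**What to change.** In 5.5 and the Survival Status row of 6.1, replace the 24-month limit for survival status by follow-up until death, withdrawal from follow-up, or one common study closure or data cut-off within the planned 54–60 months. Check the survival status of every living patient at that date. In 11.4, define OS from the start of treatment to death from any cause, and censor living patients at the last date known alive. The scan and EQ-5D schedules can stay as they are.

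The cost is an amendment, revised consent wording and a modest number of extra calls; the footnotes to 6.1 already allow follow-up by phone. No patients, scans or study time are added. The change needs to be in force before the first patients reach 24 months off treatment.

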5.6 Off Treatment Criteria

Patients can be taken off study treatment at any time at their own request with a withdrawal of informed consent, or they may be withdrawn at the discretion of the investigator for safety, behavioral or administrative reasons. The reason(s) for discontinuation from study treatment will be documented and may include:

- Disease progression as defined in Section 7.0 or evidence of clinical progression as determined by treating investigator;
- Subject has intolerable toxicity from study therapy despite supportive measures and maximum permitted dose modifications and holds per protocol;
- Patient withdraws informed consent (termination of treatment and follow-up for any reason);
- Loss of ability to freely provide informed consent through imprisonment or involuntary incarceration for treatment;
- Patient is unable to comply with protocol requirements;
- Treating physician determines continuation on the study would not be in the patient's best interest;
- Development of second malignancy (except for basal cell carcinoma or squamous cell carcinoma of the skin or Gleason ≤ 6 prostate cancer) that requires treatment, which would interfere with this study;
- Lost to Follow-up. If a research subject cannot be located to document survival after a period of 2 years, the subject may be considered "lost to follow-up." All attempts to contact the subject during the two years must be documented;
- Termination of the study by the University of Michigan;
- Patient completes protocol treatment and follow-up.

5.7 Patient Replacement

Patients who are not evaluable for objective response (as defined in Section 7.1.1) will be replaced.

6.0 SCHEDULE OF ASSESSMENTS

6.1 Time and Events Table

1 cycle (C) = 28 days (D).

Trial Period	Screening (-28 to -1 days)	C1D1	C2D1	C3D1	C4D1	Additional Cycles...	EOT ⁷	Follow-Up ⁸
							30 days from last dose (+/- 7 business days)	Every 12 weeks (+/-14 business days) for up to 24 months/death
Informed Consent	X							
Tumor tissue specimen (15 FFPE slides required; blocks preferred) identified	X							
Blood for banking		X						
History, PE, Concomitant Meds, Vital Signs ¹	X	X	X	X	X	X	X	
PT/INR, aPTT	X							
Karnofsky Performance Status	X	X	X	X	X	X	X	
Pregnancy Test for WOCBP ²	X							
Toxicity (include DLT) Evaluations ¹²	X	X	X	X	X	X	X	
CBC with differential, platelets ³	X	X ¹³	X ¹³	X	X	X	X	
COMP ⁴	X	X	X	X	X	X	X	
TSH	X	Every 12 weeks from Cycle 1 Day 1 ⁵						
QoL (EQ-5D-5L)		X	X	X		X ¹⁴		X
Pill Diary collection/handing out		X	X	X	X	X		
Tumor response assessment ⁶ (CT chest, CT or MRI abdomen/pelvis; CT or MRI brain if clinically indicated)	X			X		X ⁶		X
Treatment								
ESK98 ^{9, 10} (Cohort A and B)		X	X	X	X	X		
Nivolumab ¹¹ (Cohort B only)		X	X	X	X	X		
Survival Status								X

1. Vital signs will include weight, temperature, pulse, respirations, blood pressure; height will be obtained at screening only.
2. WOCBP: Women of child bearing potential; either urine or serum pregnancy test.
3. CBC with diff includes total WBC, hemoglobin, hematocrit and differential of the WBC including absolute counts. Other checks are at discretion of treating investigator.

4. COMP or Comprehensive metabolic profile includes sodium, potassium, chloride, bicarbonate, BUN, creatinine, AST, ALT, alkaline phosphatase, total bilirubin.
5. TSH: Every 12 weeks from Cycle 1 Day 1 (i.e. Cycle 4 Day 1; Cycle 7 Day 1, etc.).
6. Window of +/- 7 business days. Imaging will be with or without intravenous contrast, before or on associated visit. CT or MRI brain with (preferred) or without IV contrast if suspected or known brain metastases. Frequency of tumor assessments will be q2 cycles (i.e. q 8 weeks) for first 4 assessments beyond baseline and then q 3 cycles (i.e. 12 weeks) subsequently until withdrawal of consent/death/2 years from C1 D1 whichever is later. If CR/PD, should be confirmed with repeat imaging after an interval of at least 4 weeks. In follow-up, if subjects are on alternative therapies, no mandated imaging but data from routine imaging will be captured at least every 12 weeks if available (+/- 7 business days).
7. End of treatment visit may or may not be the same day as a planned study visit. If it is not on a planned study visit, the minimum assessments listed in the schedule must be completed.
8. Follow-up may be conducted by phone call or a clinic visit.
9. Study drug(s) must be started within 14 business days from time of enrollment.
10. ESK981 will only be given on days 1-5 of each week of each treatment cycle followed by 2 days off.
11. Nivolumab will be administered on Day 1 of each treatment cycle in Cohort B.
12. All Serious Adverse Events (SAEs) occurring from the initial study treatment administration through 60 days following the last dose of the study treatment should be reported to the Coordinating Center. Any SAEs occurring after 60 days following the last dose of the study treatment that are believed to be related to study drug should also be reported to the Coordinating Center.
13. CBC with diff must be obtained weekly during Cycles 1 and 2. For patients who experience no \geq Grade 3 hematological toxicity during Cycles 1 and 2, monthly blood counts will be obtained during subsequent cycles.
14. QOL obtained Cycles 1-3, 5, 7 and 9 then q 3 cycles (12 weeks) subsequently

NOTE:

All assessments have a window of \pm 3 business days unless otherwise mentioned.

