2.6 Exploratory Endpoint

2.6.1 Health-related quality of life assessment changes from baseline using EuroQoL-5D will be described using descriptive statistics.

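### EQ-5D-5L is not scheduled at the end-of-treatment visit, so patients who stop between questionnaires have no required form until 12-weekly follow-up

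*Combined protocol and SAP*

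**What the plan says.** In the section 6.1 table the EQ-5D-5L row is marked at C1D1, C2D1, C3D1, Additional Cycles and Follow-Up. It is blank at Screening, C4D1 and EOT. Footnote 14 gives the on-treatment cycles: "QOL obtained Cycles 1-3, 5, 7 and 9 then q 3 cycles (12 weeks) subsequently". That footnote does not mention EOT; the evidence for the omission is the empty cell in the row.

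The EOT visit is placed 30 days after last dose, give or take 7 business days. History and examination, Karnofsky status, toxicity, CBC and chemistry are all marked there. EOT may share a day with a planned visit. Otherwise, under footnote 7: "If it is not on a planned study visit, the minimum assessments listed in the schedule must be completed". EQ-5D-5L is not among the assessments listed in that column.

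The Follow-Up column, where EQ-5D-5L is marked, is headed "Every 12 weeks (+/-14 business days) for up to 24 months/death". The point from which the 12 weeks run is not given.

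The analysis, in the same words in sections 2.6 and 11.4, is: "Health-related quality of life assessment changes from baseline using EuroQoL-5D will be described using descriptive statistics". No timepoint, population or rule for missing forms is named.

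**The concern.** Stopping treatment is often linked to how the patient feels. Where a patient stops for toxicity or clinical decline between two questionnaires, the schedule asks for nothing until follow-up, so missing forms are likely to be related to the outcome. The objective in section 2.3 concerns patients enrolled on the study, which includes those who stop early. For a patient who stops in Cycle 1, no change from baseline can be computed unless a follow-up form is completed.

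What is at stake is how completely the quality-of-life description reflects early stoppers. The response endpoint, sample size and error rates are not affected. A form not collected at EOT cannot be recovered later.

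**Working it through.** The plan gives no numerical target for this endpoint, so there is no figure to reproduce. The check is of the schedule.

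**1. Is the EOT cell really blank?** The EQ-5D-5L row has eight cells and lines up with its neighbours. Karnofsky status is marked at EOT and blank at Follow-Up; survival status is marked only at Follow-Up; the pill diary ends at Additional Cycles. The EQ-5D-5L mark after Additional Cycles therefore belongs to Follow-Up, and EOT is empty.

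**2. When are forms due on treatment?** With 28-day cycles, days from C1D1 = (cycle − 1) × 28. Cycles 1, 2, 3, 5, 7, 9, 12 and 15 give days 0, 28, 56, 112, 168, 224, 308 and 392, that is weeks 0, 4, 8, 16, 24, 32, 44 and 56.

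**3. How old can the last form be at last dose?** At most, the interval between forms minus one day:
- Cycles 1–2: 28 − 1 = 27 days
- Cycles 3–8: 56 − 1 = 55 days
- Cycle 9 onward: 84 − 1 = 83 days

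**4. When is the next form due?** Twelve weeks is 84 days. If the clock starts at last dose, the next form comes at 84 days. If it starts at EOT, it comes at 30 + 84 = 114 days. Both are before visit windows. With a form at EOT it would come at about 30 days, which is 84 − 30 = 54 or 114 − 30 = 84 days sooner.

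**5. Longest stretch around stopping without a required form** (step 3 plus step 4):

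| Stop in | Now, clock from last dose | Now, clock from EOT | With form at EOT |
|---|---|---|---|
| Cycles 1–2 | 27 + 84 = 111 days | 27 + 114 = 141 days | 27 + 30 = 57 days |
| Cycles 3–8 | 55 + 84 = 139 days | 55 + 114 = 169 days | 55 + 30 = 85 days |
| Cycle 9 on | 83 + 84 = 167 days | 83 + 114 = 197 days | 83 + 30 = 113 days |

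In Cycle 1 the only form before the gap is the baseline itself.

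**6. Which stops fall in the gap?** Footnote 6 sets the scans: "Frequency of tumor assessments will be q2 cycles (i.e. q 8 weeks) for first 4 assessments beyond baseline and then q 3 cycles". That puts scans at Cycles 3, 5, 7, 9, 12 and 15, all of which are EQ-5D cycles. Progression seen on a scheduled scan therefore has a form due at about the same visit.

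Three kinds of stop are not aligned in this way: toxicity, clinical progression, and confirmation of immune-related progression in Cohort B. Sections 7.1 and 7.1.4.4 place the confirmatory scan 4 to 8 weeks after the first progression. After progression at Cycle 3, a scan at 4 weeks falls at Cycle 4, which has no form. After progression at Cycle 9, 4 to 8 weeks later is Cycle 10 to Cycle 11, and the next form is due at Cycle 12.

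**The case against.** Patients who stop are not lost to the questionnaire. EQ-5D-5L is marked in follow-up, section 5.5 provides that "Patients will be followed for up to 24 months after removal from treatment or until death, whichever occurs first", and footnote 8 adds "Follow-up may be conducted by phone call or a clinic visit", which eases completion by unwell patients. Scheduled scans share the questionnaire cycles, so much scan-detected progression has a form close by. The endpoint drives no decision. All of this stands, and it limits the point to stops between questionnaires and to the delay before the first off-treatment form.

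Three stronger readings are tempting, and the documents do not support them.

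- A reader might infer that change from baseline will be averaged only over patients who stay on treatment. Section 11.4 contains no such restriction, and follow-up forms are scheduled. What can be said is that the plan names no timepoints, and that any summary by treatment cycle would cover only those still on treatment.
- A reader might infer that the form nearest to stopping is always the one missing. In Cycles 1–2 the last form is at most 27 days before last dose, already nearer than an EOT form at 30 days. What is missing is an early post-treatment reading.
- A reader might take the synopsis estimate of 6 months of treatment as a median and work out how many patients remain at each cycle. The synopsis gives it only as a component of study duration.

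**Conclusion.** The point holds in a limited form. EQ-5D-5L is not required at EOT, and patients who stop between questionnaires wait about 84 to 114 days after last dose for the next scheduled form, where an EOT form would come at about 30 days. The range reflects the unstated start of the follow-up clock, and visit windows are ignored. A patient who stops in Cycle 1 has no post-baseline form before then.

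The number of patients affected cannot be derived from the documents, since no rate of stopping by reason or cycle is given. The importance is low. Quality of life is exploratory in sections 2.3 and 2.6 (although section 11.1 lists it in the paragraph on secondary endpoints), and it is descriptive, unsized and separate from any success or stopping criterion.

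**What to change.** - **Section 6.1:** mark EQ-5D-5L in the EOT column and add EOT to footnote 14. State whether the 12-week follow-up interval runs from last dose or from the EOT visit.
- **Section 11.4:** report change from baseline to EOT as its own timepoint. For each by-cycle summary, show the number of forms received and the number of patients still on treatment.

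Change to EOT should stay separate from any last-available-value summary. Because forms continue in follow-up for up to 24 months, the last value would often be a late one rather than the state soon after stopping.

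The cost is one short questionnaire at an existing visit, with no change to sample size, error rate or power. The gain is at most one extra form per treated patient, and less where a patient dies, withdraws consent or misses EOT. An EOT form does not by itself cure attrition in the by-cycle summaries, which is why the counts are needed as well.
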